2.0 STUDY OBJECTIVES

Outcomes:

- Primary outcomes: radiation exposure, time, accuracy of placement (right angle to rod).
 - Each distal interlock will be considered a separate outcome
 - The first fluoroscopy shot to localize the jig or obtain a perfect circle is considered start time. The surgeon will note the hour, minute, and seconds of the time based on the wall clock in the operating room.
 - The last shot to confirm complete seating of the screw will be considered end time. The surgeon will note the hour, minute, and seconds of the time based on the wall clock in the operating room.
- Secondary outcomes:
 - accuracy of placement (right angle to intramedullary nail).
 - Number of complete misses of the nail with the drill or the screw
 - comparison of learning curve between distal targeter and freehand techniques stratified by level of training
 - The level of training of the surgeon
 - Experience level of the surgeon
 - estimated number total number of intramedullary nails placed
 - time since the last intramedullary nail placement
 - estimated number of nails placed per month over the last year
 - number of times the surgeon has used the distal targeting system
 - Comparison of tibia vs femur antegrade nails

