4.0 STUDY DESIGN AND METHODS

This study will be a prospective, randomized control trial. Patients will be randomized to perform distal interlock screen insertion either by freehand or distal targeting for all lower extremity nails.

1. All patients undergoing femoral or tibial nailing will undergo one method of interlock placement starting on the first of the month starting with free-hand locking. The method of interlocking screw placement will then switch to jig-based screw placement at the first of the following month. The method of screw placement will alternate each week until enrollment is complete. This method of enrollment for clinical modalities that are already in common use has previously been described with the PREP-IT trials. [Slobogean et al, JAMA Netw Open 2020]
2. Due to the nature of the distal targeting jig's construction, there may be instances where its use is not possible due to interference with other surgical instrumentation, and an intraoperative decision must be made to place screws with the freehand technique. Patients randomized to the jig-based placement arm but are ultimately treated with freehand placement will be documented and reported as crossover patients (per the CONSORT framework).
3. Patients randomized to their respective groups will ultimately undergo intention-to-treat analysis.

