7.0 STATISTICAL CONSIDERATIONS

7.1 STUDY OUTCOME MEASURES

- Primary Outcome analysis: 2 tailed T-test for average length of surgery (skin to skin), average time to place 2 interlocks (start time when nail is seated and surgeon states s/he is ready to proceed with distal interlocking screw placement). Average radiation used in microGrays. Femur vs tibia average time to place 2 interlocks and average radiation exposure.
 - To compare time and accuracy of placement only data from surgeons who have performed both DT and FH techniques more than 5 times will be included.
- Secondary outcomes: t-test accuracy of screw placement (perpendicular to nail)
 - Multivariate regression evaluating predictors of time to placement
 - Level of training
 - Number of cases performed
 - Number of interlocking screws placed
 - Time since last case
 - Learning curve assessment
 - Time of each interlocking screw placement will be correlated with number of interlocking screws placed
 - Time of procedure and accuracy of placement will be analyzed in increments of 5 cases to evaluate for number of cases required to reach plateau
 - Data will be stratified by level of training

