7.2 SAMPLE SIZE CONSIDERATIONS

- Power: Based on a more recent paper from Konda et al, the average time for distal interlocking screw placement was 616 seconds in the control and 344 seconds in the distal targeting with an SD of 192 seconds. This suggests that a total of 30 patients would need to be enrolled for each cohort to detect a 44% decrease in the amount of time required for distal interlocking screw placement with the distal targeter with 90% power at 5% significance. (sealedenvelope.com power calculator on-line)
 - Estimating a 75% participation rate, we intend to enroll 60 patients (30 in each cohort – tibia and femur surgeries) that meet the sub-study criteria
 - Given that 9% of the currently enrolled patients (included in the main study) will not meet the sub-study criteria (retrograde nails instead of antegrade), we intend to enroll a total of 66 total patients for this study (includes patients for main study and sub study).

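### The femur-versus-tibia comparison does not say how technique is handled; one model with technique, bone and their interaction would be more precise and answer more

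*Combined protocol and SAP*

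**What the plan says.** The primary analysis entry in section 7.1 opens with "Primary Outcome analysis: 2 tailed T-test for average length of surgery (skin to skin" and goes on to time for two interlocks and radiation. It closes with "Femur vs tibia average time to place 2 interlocks and average radiation exposure". Nothing there says whether the bone comparison pools the techniques, separates them or adjusts for technique. The regression listed later in 7.1 has as predictors training level, cases performed, screws placed and time since the last case. Neither technique nor bone is among them.

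Section 2.0 lists "Comparison of tibia vs femur antegrade nails" as a secondary outcome, also without reference to technique.

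Section 7.2 takes its planning values from a published comparison of the two techniques: "616 seconds in the control and 344 seconds in the distal targeting with an SD of 192 seconds". It concludes that "a total of 30 patients would need to be enrolled for each cohort" and then describes the cohorts by bone: "Estimating a 75% participation rate, we intend to enroll 60 patients (30 in each cohort – tibia and femur surgeries".

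Section 4.0 assigns technique by calendar period ("The method of screw placement will alternate each week until enrollment is complete"). No stratification by bone is stated.

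**The concern.** A two-sample t-test with bone as the grouping factor has no place for technique. If all cases enter it, each bone group mixes two populations whose means the plan expects to lie 272 s apart. That known source of variation then goes into the error term. The bone contrast also depends on how many jig cases happen to fall among femurs and among tibias.

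The trial's stated purpose is to compare two techniques. A femur-versus-tibia test, pooled or run within one technique, does not show whether the jig's effect is the same in both bones, and no other listed analysis does. Because the text is silent, the choice between a pooled, a within-bone and an adjusted analysis could be made after the data are seen.

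**Working it through.** **Inputs from section 7.2:** means 616 and 344 s (difference 272 s), SD 192 s, 90% power, 5% significance, 30 per bone cohort, 75% participation.

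**Assumptions:** a 50:50 technique mix; 30 analysed per bone; the same within-technique SD in both bones. The documents give none of these.

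**1. The plan's own figure.** Patients per technique = 2 × (1.960 + 1.282)² × 192² / 272² = 10.5, rounded up to 11. Two techniques need 22, and 22 / 0.75 = 29.3, rounded up to 30. So 30 reproduces as the total for one bone cohort, about 15 per technique. It does not reproduce as 30 per technique arm: one- or two-sided tests at 80% to 95% power give 7 to 13.

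**2. SD within a bone if techniques are pooled.** With jig share p, SD = √(192² + p(1 − p) × 272²).
- p = 0.5: √(36,864 + 18,496) = √55,360 = 235.3 s. Variance ratio 55,360 / 36,864 = 1.50.
- p = 0.4 or 0.6: 234 s. p = 0.3: 229 s.

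**3. Standard error of the bone difference, 30 v 30.**
- Pooled: 235.3 × √(2/30) = 60.8 s.
- Technique removed from the error: 192 × √(2/30) = 49.6 s.
- Bone difference detectable with 90% power: 3.242 × 60.8 = 197 s pooled, against 3.242 × 49.6 = 161 s.
- If the 75% participation leaves 22 analysed per bone: 235.3 × √(2/22) = 70.9 s pooled, against 192 × √(2/22) = 57.9 s.

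**4. Chance differences in jig share.** Under independent 50:50 assignment, the SD of the difference in share between bones is √(2 × 0.25 / 30) = 0.129, which is 0.129 × 272 = 35.1 s. Then √(49.6² + 35.1²) = 60.8 s. The pooled standard error therefore already contains this component.

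**5. A realised gap in share.** The time contrast moves by 272 × 0.10 = 27 s for each 10-point gap in jig share between bones.

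**6. Technique-by-bone interaction, 15 per cell.** SE = 192 × √(4/15) = 99 s. The difference in jig effect detectable with 90% power is 3.242 × 99.1 = 321 s, more than the whole 272 s effect. With 11 per cell, SE = 192 × √(4/11) = 116 s.

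**7. Radiation.** The documents give no planning mean or SD for radiation, so no corresponding calculation is possible.

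**The case against.** The strongest reply is that the plan never says it pools. Step 1 shows that 30 per bone fits a comparison of techniques within each bone. If that is the intended analysis, the variance inflation does not arise. This stands: pooling is the literal reading of 7.1, not a documented decision. It does not remove the need for a change, because 7.1 then fails to describe the analysis that 7.2 was sized for.

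A reader might infer that the bone comparison is biased by technique mix. The documents do not show this. Under chance assignment the expected bone difference is unaffected, and the imbalance is already in the 60.8 s standard error, so it is not a second harm. Systematic bias would need jig share to depend on bone. Calendar allocation without stated stratification by bone leaves that possible, but nothing shows that it happens.

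A reader might also infer that the plan misses an objective by not testing whether the jig's benefit differs by bone. No section states that aim, and a descriptive comparison of bones is legitimate. Nor does the plan claim any power for the bone contrast, so no such claim is broken.

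Finally, the interaction will be imprecise at this sample size. That is correct, and it is a reason to label the interaction exploratory.

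**Conclusion.** Section 7.1 leaves the handling of technique in the femur-versus-tibia comparison unspecified. If cases are pooled, the planning figures imply a variance 50% larger than necessary for time, and a standard error of 60.8 s instead of 49.6 s. This assumes a 50:50 mix and 30 analysed per bone. At 30% jig share the pooled SD is 229 s rather than 235 s. Fewer analysed patients raise both standard errors in the same proportion. The number analysed could fall because of participation, or because 7.1 limits the time comparison to surgeons with more than five uses of each technique.

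The finding for radiation is qualitative only. If within-bone comparisons are intended, the fault is that 7.1 omits them. On either reading, the difference in technique effect between bones goes unestimated. This is a low-cost improvement in specification; it does not show that the trial's main technique comparison is invalid.

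**What to change.** In section 7.1, replace the femur-versus-tibia t-tests with one linear model per outcome (time, radiation) containing assigned technique, bone and technique-by-bone. Assigned technique keeps the model consistent with the intention-to-treat statement in 4.0. Report:

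- the technique-adjusted bone difference, taken from the main-effects model or from centred coding (with reference coding and an interaction in the model, the bone coefficient describes only one technique);
- the technique effect within each bone;
- the interaction with its confidence interval, labelled exploratory, noting the expected standard error of about 99 s for time at 15 per cell and more if fewer are analysed.

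State in 7.2 that the cohorts are bones, each split between techniques, if that is what is meant. Reconcile the status of the bone comparison between 7.1 (primary) and 2.0 (secondary).

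The cost is wording only. Assigned technique follows from the allocation and bone from the procedure, so no new data are needed.

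### The promised comparison of learning curves between techniques has no stated analysis, and the screw-level correlation ignores patients and surgeons

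*Combined protocol and SAP*

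**What the plan says.** Section 2.0 (Study objectives) lists among the secondary outcomes a "comparison of learning curve between distal targeter and freehand techniques stratified by level of training". It also states "Each distal interlock will be considered a separate outcome". The experience variables it names include "estimated number total number of intramedullary nails placed" and "number of times the surgeon has used the distal targeting system".

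Section 7.1 (Study outcome measures) gives the analyses:

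- "Multivariate regression evaluating predictors of time to placement", with four listed predictors: training level, cases performed, screws placed and time since the last case.
- "Time of each interlocking screw placement will be correlated with number of interlocking screws placed".
- Procedure time and accuracy examined in blocks of five cases, to find a plateau.
- "Data will be stratified by level of training".

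The same section limits the comparison of time and accuracy to surgeons with more than five uses of each technique. Section 4.0 commits to intention-to-treat and says that jig patients who end up with freehand placement are documented as crossovers. The variable list in section 5.3 covers identifiers, date and length of surgery, injury, procedure and radiation. It has no surgeon identity, training level, screw-level time or experience count.

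**The concern.** A comparison of learning curves asks whether time falls faster with experience under one technique than under the other. That is a technique-by-experience contrast, or two separate curves set against each other. The regression and learning-curve lines contain neither. Followed as written, they describe how time relates to experience with both techniques mixed together, and the secondary objective goes unanswered.

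The correlation has a second weakness. Two screws in one patient share anatomy, nail and operating conditions, and all of one surgeon's screws share that surgeon's speed. Treating them as independent overstates the information. Surgeons who place more screws, or enter with higher counts, also sit at the high end of the horizontal axis. If they happen to be faster or slower throughout, the pooled plot shows a slope with no learning in it.

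**Working it through.** **The plan's own figure.** Section 7.2 gives 616 s against 344 s with SD 192 s, 90% power and 5% significance. Per arm, n = 2 × (1.960 + 1.282)² × 192² / 272² = 10.5, so 11. Two arms make 22 per bone cohort; 22 / 0.75 = 29.3, so 30; two cohorts make 60; 60 / 0.91 = 65.9, so 66. The figure reproduces. It is sized on a difference in mean time and has no input for learning curves or clustering.

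**Objective against analysis.** The objective has three parts: technique, experience and training level. The regression has experience and training. The correlation has experience. The five-case blocks have experience and do not say whether they are formed per surgeon or per technique. The stratification has training. Technique is in none of them.

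**Patient clustering.** Section 7.1 refers to "average time to place 2 interlocks", so I take 66 × 2 = 132 screws. With within-patient correlation ρ (assumed), the design effect is 1 + (2 − 1)ρ and the real error of a nominal 5% test is 2[1 − Φ(1.96/√(1 + ρ))].

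- ρ = 0.3: 132 / 1.3 = 102 effective screws, real error 8.6%.
- ρ = 0.5: 132 / 1.5 = 88 effective screws, real error 11.0%.

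Simulation of the Pearson test gave 8.4% and 10.9%.

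**Surgeon clustering added.** Simulated with no true learning, 2,500 runs per setting, 4, 6 or 10 surgeons, patient ICC 0.3 and surgeon ICC 0.1 to 0.3 (all assumed). Entries are false positives at a nominal 5%:

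| Starting screw counts | Pooled | Within one of two training strata |
|---|---|---|
| All zero | 11% to 18% | 10% to 15% |
| Spread over 0–40 | 22% to 41% | 15% to 30% |
| Spread over 0–200 | 23% to 58% | 22% to 47% |

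A separate simulation with 4 to 12 surgeons and surgeon ICC 0.1 to 0.2 gave 10% to 14% from zero and 22% to 40% with starts spread over 0–59. Stratifying by training reduces the problem without removing it, because a stratum still holds several surgeons.

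**Leaving technique out of the regression.** The bias in the experience slope is the technique effect times the slope of the technique indicator on experience. It is zero if mean experience is equal between arms. For equal arms, a 10-use gap and experience uniform over 40 uses within each arm (assumed), its size is 272 × (10/4) / (40²/12 + 10²/4) = 680 / 158.3 = 4.3 s per use. Over 100 uses it is 680 / 858.3 = 0.8 s, and over 200 uses 680 / 3358.3 = 0.2 s. Simulated false positives, with training and time since last case in the model, were 33%, 10% and 6%. With no gap, or with technique added, they were about 5%.

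**Five-case blocks.** 66 / 2 = 33 cases per technique. Over 4, 6 or 10 surgeons that is 8.3, 5.5 or 3.3 each, so on average at most one full block per surgeon and technique.

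**The case against.** The sponsor may well intend separate curves for each technique and have left that unsaid. The plan names no significance test for the correlation, so the error rates apply only if one is attached. The documents give no intraclass correlation, number of surgeons or starting counts, and the upper end of 58% needs a surgeon ICC of 0.3 with starts spread over 0–200. The analysis is secondary, and precision would be low under any model. All of this stands, and it limits the size of the point.

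Three stronger readings are tempting and should not be drawn:

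- A reader might infer that no analysis in section 7.1 involves technique. The restriction on surgeons names both techniques, and the t-tests evidently compare them. The gap is confined to the regression and learning-curve lines.
- A reader might infer that omitting technique always biases the experience slope. It does so only if experience is counted per technique and differs between arms.
- A reader might infer that the regression is sure to be collinear because it lists both cases and screws. That follows only if both count the same cumulative experience; the screw count could mean screws in the current case.

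What the objection does not remove is that an objective stated as a contrast between techniques is met by analyses that do not contain technique.

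**Conclusion.** The concern holds for the regression and learning-curve analyses. The promised contrast has no stated analysis; this follows from the text and needs no assumption. The independence problem in the correlation also follows from the text, since several screws come from each patient and each surgeon. Its size does not: about 8% to 12% false positives for patient ICC 0.3 to 0.5, 11% to 18% with surgeon ICC 0.1 to 0.3 from zero counts, and 22% to 58% with unequal starts, all under assumed inputs. Unequal starts are plausible, because section 2.0 plans to record how experience differs between surgeons. The change should be made while data fields can still be set.

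**What to change.** 1. Replace the pooled correlation and the regression without technique by one linear mixed model for screw-level time. Fixed effects: technique, prior cases with that technique, their interaction, level of training, time since last case, and bone. Random intercepts for patient and surgeon, with a small-sample method such as Kenward-Roger. Enter experience once if cases and screws count the same thing.
2. Add a random surgeon slope for experience where it can be estimated. Otherwise state that the model assumes a common learning rate and that its intervals may be too narrow. In a simplified simulation of the intercept-only model, an assumed between-surgeon SD of 50, 100 or 150 s in jig learning over 8 cases gave 8% to 12%, 15% to 26% and 22% to 35% false positives.
3. For results by training level, add the technique × experience × training term or fit separate models by level. Report an exploratory estimate with a 95% CI, and show the five-case blocks by technique descriptively.
4. Model technique used, label the analysis as-treated, and note that crossovers are selected, because section 4.0 attributes them to interference with the jig. Keep the randomized comparison intention-to-treat.
5. State that the restriction to surgeons with more than five uses of each technique applies to the technique comparisons of time and accuracy, as section 7.1 says, and not to the learning-curve model, where it would remove the early part of the curve.
6. Add to section 5.3: surgeon ID, technique used, training level, screw-level times, time since last case, and prior counts for each technique. Several are already implied by sections 2.0, 4.0 and 7.1.

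The cost is SAP wording, somewhat more analysis and data entry, and no extra patients. Precision will be low. With random intercepts only and experience entered linearly, the simulated 95% CI for the difference in learning over 8 cases was about ±136 to 184 s, against a planned mean difference of 272 s, and wider within a training level. Variation in learning rates would widen it further. The result estimates a difference; it cannot confirm one.

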3.5 SUBJECT RECRUITMENT

Patients will be recruited from all full-time orthopaedic trauma faculty. The treating surgeon and/or clinical research associate will approach patients in person to recruit, enroll and consent them for the study. No advertisement will be used for this study.

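### The predictor regression does not say how repeated cases per surgeon are handled, so an ordinary fit would overstate the evidence for a training-level effect whenever surgeons differ within a level

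*Combined protocol and SAP*

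**What the plan says.** Section 7.1, under secondary outcomes, plans a "Multivariate regression evaluating predictors of time to placement". The listed predictors are level of training, number of cases performed, number of interlocking screws placed and time since the last case. Technique is not listed. The same section also correlates the time for each screw with the number of screws placed, and stratifies by level of training.

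Section 2.0 makes training a property of the operator ("The level of training of the surgeon") and, on the unit of outcome, says "Each distal interlock will be considered a separate outcome". Section 7.1 elsewhere works with the "average time to place 2 interlocks", so both case-level and screw-level rows are possible.

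On who operates, section 3.5 says only "Patients will be recruited from all full-time orthopaedic trauma faculty". The number of surgeons or trainees is not stated. The planned size is in section 7.2: "we intend to enroll a total of 66 total patients for this study".

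Nothing in the protocol or its statistical section provides a surgeon random effect, a clustered variance, a surgeon-level summary or any other allowance for repeated cases per surgeon or repeated screws per patient. The variable list in section 5.3 names neither the operating surgeon nor the training level.

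**The concern.** One centre plans 66 patients, so surgeons will contribute repeated cases. Suppose two surgeons at the same training level differ in habitual speed. All of one surgeon's cases then share that difference, and further cases from the same person add little information about the level as a whole. Ordinary regression takes its error from the residual scatter of rows and treats every row as new information on training. Its standard error for the training coefficient is then too small, and a small p-value may reflect one or two quick or slow individuals.

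Stratifying by training level does not help, because the ignored variation lies between surgeons within a level. At stake is the conclusion on training level, a named secondary aim.

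**Working it through.** **The plan's own figures.** Section 7.2 gives means of 616 s and 344 s (difference 272 s), SD 192 s, 90% power and 5% significance; section 7.1 specifies a two-tailed test. Per arm: 2 × (192 × (1.960 + 1.282) / 272)² = 10.5, so 11. Two arms make 22 per tibia or femur cohort; 22 / 0.75 = 29.3, so 30; 2 × 30 = 60; 60 / 0.91 = 65.9, so 66. The stated numbers reproduce if a cohort is a bone and the 75% participation is already inside the 30. They size the time comparison. No figure is given for the predictor regression.

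**Assumptions.** 60 cases spread evenly over J surgeons, m = 60/J cases each; two training levels with no true difference; surgeon ICC 0.05, 0.10 or 0.20. J and the ICC are not in the documents, so both are shown as ranges.

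**Formula.** For a predictor constant within surgeon, the design effect is D = 1 + (m − 1) × ICC. The ordinary standard error is too small by a factor √D. The approximate true size of a nominal 5% test is 2 × (1 − Φ(1.96/√D)). For J = 5 and ICC 0.10: D = 1 + 11 × 0.10 = 2.10, √D = 1.45, size 17.6%.

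| J (m) | √D at ICC 0.05 / 0.10 / 0.20 | Size by formula | Size by simulation |
|---|---|---|---|
| 5 (12) | 1.24 / 1.45 / 1.79 | 11.5 / 17.6 / 27.3% | about 11 / 18 / 28% |
| 12 (5) | 1.10 / 1.18 / 1.34 | 7.4 / 9.8 / 14.4% | about 7 / 10 / 15% |
| 20 (3) | 1.05 / 1.10 / 1.18 | 6.2 / 7.4 / 9.8% | about 6 / 7 / 10% |

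A test on surgeon means stays at about 5% in the simulated settings. With zero ICC the case-level test is also correct, at about 5%.

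**Technique omitted.** The predictor list does not include technique. If it stays out, the expected 272 s difference enters the residual. With half the cases on each technique it adds 272²/4 = 18,496 to 192² = 36,864, giving 55,360. The ICC is then diluted by 36,864/55,360 = 0.67, to 0.033, 0.067 and 0.133. By formula, sizes become 9.4 / 13.6 / 21.2% (5 surgeons), 6.6 / 8.2 / 11.3% (12) and 5.8 / 6.6 / 8.2% (20). Simulation gives about 10 / 14 / 21%, 7 / 8 / 11% and 5-8%. If technique is omitted but exactly balanced within each surgeon, rates are lower: 6 / 10 / 18% for 5 surgeons and 3 / 5 / 8% for 12.

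**Screws as rows.** With two screws per case treated as independent, and an assumed extra within-case correlation of 0.3, the rates are 21 / 31 / 44% for 5 surgeons and 12 / 14 / 20% for 20. Even with zero surgeon ICC the rate is about 9%.

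**Where 5 surgeons comes from.** Section 7.1 says that, for time and accuracy, "only data from surgeons who have performed both DT and FH techniques more than 5 times will be included". More than 5 of each means at least 6 + 6 = 12 cases per surgeon, and 66/12 = 5.5, so at most 5 surgeons. This holds only if the count is made within the trial and the filter is extended to the regression.

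**The case against.** - **Independent rows are not stated.** A reader might infer that the plan commits to treating each case or screw as independent. It does not: it is silent on unit and variance. The supportable point is the omission. It still matters, because an unqualified regression together with the separate-outcome rule permits the ordinary analysis.
- **Five surgeons.** A reader might infer that at most 5 surgeons can supply data. The filter sits under the primary outcome and concerns time and accuracy. Its wording can mean lifetime experience, and applying it here would remove the novices that a learning-curve analysis needs. If trainees place screws, operators may outnumber faculty. The 5-surgeon row is therefore one conditional scenario, and with 20 surgeons the inflation is modest.
- **All predictors affected.** A reader might extend the point to every experience variable. Cases performed, screws placed and time since the last case can change within a surgeon, and a simulated within-surgeon case-order covariate rejected at only about 3-5%. The computed support is for training level alone. Even that is only essentially constant, since a trainee may advance during the year.
- **The ICC may be near zero.** Then a case-level fit has no inflation. But the plan itself expects operators to differ, since it tracks experience, recency and learning. Experience covariates may absorb part of the difference, though not necessarily individual speed.
- **A mixed model is not a complete cure.** With 5 surgeons in two levels, the surgeon variance is estimated as zero in about 39%, 26% and 14% of simulated trials at ICC 0.05, 0.10 and 0.20. The model then reverts to ordinary regression. This stands, and a fallback is needed.
- **It is secondary.** This also stands: section 7.1 sets no significance threshold for this analysis, and one coefficient is affected.

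**Conclusion.** The concern holds as an omission that affects the training-level contrast. An ordinary regression, which section 7.1 permits, understates the standard error for training level whenever surgeons differ within a level. With case-level rows and ICC 0.05 to 0.20, the true size of a nominal 5% test runs from about 6% (20 surgeons, lowest ICC) to about 28% (5 surgeons, highest ICC). Omitting technique lowers this to about 5-21%, and screw-level rows raise it. The size rests on assumed surgeon numbers, ICC, an even spread of cases and two training levels. Neither the device comparison nor the predictors that vary within a surgeon are called into question by this point. It should be corrected before analysis, but it does not threaten the main conclusion of the trial.

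**What to change.** In section 7.1, replace the regression item with wording such as:

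*Predictors of placement time will be analysed in a linear mixed model with technique as a fixed effect, a random intercept for the surgeon who placed the screws (and a random intercept for patient if rows are screws), and Satterthwaite or Kenward-Roger degrees of freedom. The number of surgeons at each training level will be reported. If the surgeon variance is estimated as zero, or a level has fewer surgeons than a pre-stated minimum, the training-level contrast will be based on surgeon means or reported descriptively without a p-value.*

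The minimum number of surgeons is the sponsor's choice and should be fixed before the data are analysed. State whether rows are cases or screws, and whether the filter on surgeon experience applies to this analysis. Ordinary cluster-robust errors are not a substitute, since they are unreliable with about 5 clusters.

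In section 5.3, add an identifier for the operating surgeon and the training level at the time of surgery; the model cannot be fitted without them.

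The cost is a few lines of text, added data fields and a standard model. Intervals for training level will be wider, and with very few surgeons that contrast may be descriptive only.
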